- Swallowing disorders by modified Cowling score (liquids/solids/both/not);
- Presence of undernutrition (severe/moderate/minimal/no);
- Presence of a nasogastric tube (yes/no);
- Presence of a percutaneous gastrostomy (yes/no);
- Oral feeding resumed (yes/no).

For data collection regarding the ICU hospitalisation prior to DIFFICULT-TO-WEAN UNIT hospitalisation, this will be done on the basis of hospitalisation reports and, if necessary, by requesting additional information through telephone calls to the ICU services or the attending physician.

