10.1 Number of subjects needed

The calculation of the number of subjects required is based on the number of explanatory variables to be included in the multiple logistic regression model to determine the factors associated with successful decanulation. The "1 variable per 10 events" rule is applied. (23) We anticipate 6 variables to be included in the final multivariate predictive model, after selection of variables in univariate analysis, based on an estimated 60% success of decanulation (retrospective estimate on data available in the department), i.e. a necessary number of subjects of 100 patients.

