10.3 Main objective

Patients will be classified into 2 groups: success or failure of decanulation. The variables collected will be compared between the 2 groups by the appropriate tests according to the type of variables (quantitative or qualitative) and their distribution. The results of these comparisons will be used to select the variables showing a difference between the 2 groups (p < 0.20) for inclusion in the multivariate logistic regression. (24)(25)

The previously selected ultrasound variables will be included in the model predicting the success of decanulation. Multiple logistic regression with variable selection using the Akaike information criterion (AIC) method will be used. The presence of multicollinearity between variables will also be investigated and the variable eliminated if necessary.

11 Expected results in terms of scientific and professional advances

This study will determine the factors contributing to the success of decanulation in patients admitted to DIFFICULT-TO-WEAN UNIT after a prolonged ICU stay. The evaluation of these success factors will provide data that is still lacking due to the lack of literature in specialised post-resuscitation ventilatory weaning facilities.

This information may be useful in the post-resuscitation follow-up and in the prioritisation or not of early rehabilitation in these patients.

12 Expected benefits and risks for patients

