13.6 Information note and express consent

In accordance with Article L.1122-1 of the Public Health Code, the information provided to the persons who are to be involved in the research is the subject of a written document submitted in advance to the personal protection committee. The ethical opinion of the CPP Ouest III has been requested.

The investigator at the centre offers the patient, or a relative if the patient is incapacitated, to participate in the study. The investigator informs the patient orally of the terms of the study and gives him/her the information note. If the patient gives free, informed and express oral consent to participate in the protocol, the information given orally and in writing, as well as the collection of oral consent, will be recorded in the patient's medical record.

In the event that a relative of the patient has given consent, as soon as possible, the patient will be informed of the research and asked for oral consent for the possible continuation of the research.

Patients are free to participate or withdraw from the study at any time in accordance with Article 21 of the GDPR. Data collected until the patient withdraws consent will be used unless the patient expressly requests otherwise. The withdrawal of consent by the patient and the agreement to use or not the data previously collected will be traced in the patient's medical file.

When the research is completed, the person who is to be the subject of the research may be informed of the overall results of the research in a manner to be specified in the information document.

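### The primary model in 10.3 has no common patient set and no rule for missing covariates, and several candidate factors exist only in patients who progress, so a default fit would lose patients, mainly failures.

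*Combined protocol and SAP*

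**What the plan says.** - **Selection (10.3).** All collected variables are compared between the success and failure groups, and those with p < 0.20 go forward. Then: "Multiple logistic regression with variable selection using the Akaike information criterion (AIC) method will be used". Sections 10.2 and 10.3 give no analysis set, complete-case rule, imputation or common set of patients for the models compared.
- **Size (10.1).** "We anticipate 6 variables to be included in the final multivariate predictive model", "based on an estimated 60% success of decanulation", with ten events per variable, "i.e. a necessary number of subjects of 100 patients". The summary also gives 100 as the number of patients.
- **Missing data (9.2.2).** The plan gives only retrieval steps. Gaps are put to the patient or a relative, and for the earlier ICU stay, "if necessary, by requesting additional information through telephone calls to the ICU services or the attending physician".
- **Withdrawal (13.6).** "Data collected until the patient withdraws consent will be used unless the patient expressly requests otherwise".
- **Candidates tied to progress (4.1).** The list includes the swallowing score (done, under 7.5, once several hours a day off the ventilator are tolerated), time to 24-hour de-ventilation, time from there to successful decanulation, and fibroscopy abnormalities. Section 7.6 places the fibroscopy before decanulation, and 9.3 records whether it was performed.
- **Candidate tied to responsiveness.** Appendix 1 limits CAM-ICU to patients who can open their eyes and squeeze a hand on request. Section 9.1.2 expects some patients to arrive sedated.

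**The concern.** A standard logistic fit omits any patient who lacks a value for a covariate in the model. If the gaps were few and scattered, this would be a modest loss of precision. Here some gaps follow from the outcome process itself. A patient who never comes off the ventilator has no time to 24-hour de-ventilation, probably no pre-decanulation fibroscopy, and certainly no time to successful decanulation. These patients belong to the failure group if success is judged among all included patients, as in 4.2. A model containing such a factor compares successes with the few failures who nearly succeeded, and so answers a different question from the main objective.

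A second problem concerns AIC. AIC values are comparable only between models fitted to the same patients, because each added patient increases −2 log-likelihood. The plan does not secure that.

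The list of factors associated with success is the study's main result. As the plan stands, that list and the patients behind it would depend on a software default or on a choice made after the data are seen.

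**Working it through.** **1. The plan's own figure.** N = variables × events per variable / success proportion = 6 × 10 / 0.60 = 100. This reproduces 10.1 exactly. It implies 60 successes and 40 failures, and nothing is added for incomplete patients.

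**2. Candidates that exist only in part of the cohort.**

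| Factor in 4.1 | Who can have a value | Source |
|---|---|---|
| Swallowing score | Patients tolerating several hours off the ventilator | 7.5 |
| Time to 24-hour de-ventilation | Patients who reach it | 9.3 |
| Fibroscopy findings | Patients in whom it was performed | 7.6, 9.3 |
| Time from 24-hour de-ventilation to successful decanulation | Successes only | 4.1, 9.3 |
| CAM-ICU on admission | Responsive patients | Appendix 1 |

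The fourth factor has essentially no values among failures, so it cannot be compared between the groups at all. A complete-case model containing it would have at most about 60 patients and essentially no failures.

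**3. Size of the loss if fibroscopy is a candidate.** The inputs are 60 expected successes (10.1) and a decanulation failure rate of 2–25% (section 1). Two assumptions are needed: the 2–25% applies per decanulation attempt, and fibroscopy is done only in patients who are then decanulated.

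- Patients decanulated = 60 / (1 − failure rate).
- At 2%: 60 / 0.98 = 61.2, so about 61 patients and 1 failure.
- At 25%: 60 / 0.75 = 80, so 80 patients and 20 failures.

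The complete-case set would therefore have about 61–80 patients with 1–20 failures, against 100 patients with 40 failures in the full cohort.

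**4. Sporadic gaps.** The documents give no missing-data rate, so the rates here are assumptions. If each of 6 variables is missing independently in a share m of patients, the complete patients number 100 × (1 − m)^6.

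| m | Complete patients | Successes | Failures |
|---|---|---|---|
| 1% | 94 | 56 | 38 |
| 2% | 89 | 53 | 35 |
| 5% | 74 | 44 | 29 |

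If gaps cluster in the same patients, fewer are lost.

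**5. AIC on different rows.** At 60% success each patient adds −2[0.6 ln 0.6 + 0.4 ln 0.4] = 1.346 to the null −2 log-likelihood. Losing two patients (2 × 1.346 = 2.69) therefore outweighs the AIC penalty of 2 for one extra variable. The effect was simulated with 100 patients, 60 successes, one true predictor with a 0.4 SD difference, and one pure-noise candidate with 5% missing at random. With the p < 0.20 screen applied first, the noise variable entered in about 20% of trials when each model used its own rows, against about 15% on common rows.

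**The case against.** **AIC distortion.** A reader might infer that AIC would almost always pick an incomplete noise variable. Without the screen, the same simulation gives about 97% on own rows against about 14–17% on common rows. But 10.3 applies the p < 0.20 screen first, and a noise variable passes it only about one time in five. The difference under the actual plan is about 5 percentage points. Software may also prevent it. In a trial of R's standard step() function (version 4.3.3; the plan names 3.6.1), backward selection stopped with an error when the row count changed, and forward selection compared candidates on common rows. Comparing models by hand, or in Stata, remains possible, but nothing in the documents indicates it.

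**Scattered gaps.** A reader might also infer that ordinary missing values alone leave far fewer than 100 patients. The documents give no rate, and they do not say how many variables will pass the screen. At 1–2% missing in six variables the loss is only 6–11 patients. The retrieval steps in 9.2.2 reduce gaps.

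**Withdrawal.** By default 13.6 keeps the data. If a patient asks for removal, that patient leaves every model equally, which favours no variable.

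**Timing of the swallowing score.** Section 9.2.2 and the 9.5 table list it at inclusion, which could mean that every patient has one. Section 7.5 makes it conditional on tolerating time off the ventilator, and all patients are ventilated on admission. The passages need reconciling.

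These arguments limit the AIC and scattered-gap parts. They do not touch the factors that cannot exist for patients who fail to progress, or the absence of any rule for them.

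**Conclusion.** The point holds as a gap in the primary analysis: 10.3 does not define the patients modelled or the handling of missing covariates, while 4.1 offers candidates that are absent mainly in failures. Followed with software defaults, the plan can fit its primary model on a selected subset with too few failures, and the 100 of 10.1 would not be the number analysed.

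The size depends on which candidates survive selection. With fibroscopy in the model, about 1–20 failures remain instead of 40. That rests on the two assumptions in step 3 of the working and on counting never-decanulated patients as failures, which 4.2 implies but 10.3 does not spell out. With only sporadic gaps in six variables, the loss is 6 to 26 patients at assumed rates of 1–5%. AIC on unequal rows is a real but secondary risk.

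**What to change.** **In 10.3:**
- Limit candidates for the primary model to factors that can be measured in every included patient. Report the others descriptively, or in a separate analysis of decanulated patients.
- Fix one common patient set before AIC selection begins.
- Handle sporadic missing values in the retained candidates by multiple imputation with the outcome in the imputation model. Keep the candidate list short, because about 40 failures will not support a large imputation model. State in advance how selection is combined across imputed sets.
- Give the complete-case fit as a sensitivity analysis.

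**In 10.1:** state that 100 is the number enrolled, and commit to reporting the numbers of patients and failures actually modelled. This does not restore any lost size, but it makes the loss visible.

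**Cost:** wording in the statistics section and modest extra analysis in R or Stata, both already named in 10.2. No new data are needed. The real downside is that some factors listed in 4.1 leave the primary model.

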12.1 Minimal risks and constraints added by the research

The risks and constraints for the patient will be minimal.

They are mainly related to the extra time the patient will spend on the initial assessment by the physiotherapy team with the ultrasound. Ultrasound is a non-invasive, non-irradiating and totally painless tool.

The other procedures are an integral part of the conventional management of tracheostomised patients in DIFFICULT-TO-WEAN UNIT.

12.2 Expected patient benefits

This study will improve our knowledge of the factors involved in the success of ventilatory weaning in tracheostomised patients.

This will provide information on the elements involved in the success of decanulation in this patient population in order to best adapt the management in early rehabilitation and potentially adapt the therapeutic conduct.

The data collected will also provide information on the clinical and biological profile of patients admitted to DIFFICULT-TO-WEAN UNIT.

13 Ethical and regulatory aspects

The Forcilles-Fondation Cognacq-Jay hospital promoter and the person(s) directing and supervising the research undertake to ensure that this research is carried out in accordance with law n°2004-806 of 9 August 2004 relating to public health policy and the regulatory provisions in force (articles L.1121-1, L.1121-2 and L.1121-3 of the Public Health Code. The data recorded during this research will be subject to computerised processing in compliance with law n°78-17 of 6 January 1978 relating to information technology, files and freedoms, amended by law n° 2018-493 of 20 June 2018 (decree n° 2018-687 of 1° August 2018) and order n° 2018-1125 of 12 December 2018.

The research will be conducted in accordance with this protocol.

13.1 Role of the promoter

The research commission of the Forcilles-Fondation Cognacq-Jay hospital, promoter of this research, submits the file to the opinion of the relevant Comité de Protection des Personnes (CPP) (CPP Ouest III) whose opinion will be notified in the information note intended for the persons concerned.

The natural or legal person who initiates the research, manages it and ensures that it is financed is called the sponsor.

13.2 Submission to the PPC

This research will be submitted to a Committee for the Protection of Individuals, which will be drawn by lot within the framework of the "Jardé law" (article L.1121-4 of the Public Health Code, decree no. 2016-1537 of 16 November 2016, which came into force on 18 November 2016).

The opinion of the above-mentioned committee is notified in the information note intended for the persons concerned. A copy of this opinion and a summary of the research will be sent to the ANSM.

13.3 Data protection

This research is subject to law n°78-17 of 6 January 1978 relating to information technology, files and freedoms as amended by law n° 2018-493 of 20 June 2018 (decree n° 2018-687 of 1 August 2018). Information on the rights of persons participating in this research (right of access and rectification, right to object to the transmission of data covered by professional

secrecy likely to be used in the context of this research) is included in the information note intended for the patient.

A reference methodology specific to the processing of personal data carried out in the context of biomedical research defined by Law 2004-806 of 9 August 2004 as falling within the scope of Articles L.1121-1 et seq. of the Public Health Code was updated by the CNIL in May 2018 (Deliberation No. 2018-153 of 3 May 2018) following the publication of European Regulation No. 2016/679 (General Data Protection Regulation). This methodology allows a simplified declaration procedure when the nature of the data collected in the research is compatible with the list provided by the CNIL in its reference document. This study is part of the MR001 reference methodology to which the Forcilles-Fondation Cognacq-Jay hospital has committed to comply.

13.4 Insurance

The Sponsor takes out insurance covering its own civil liability and that of any person involved in the performance of the research for the entire duration of the research, regardless of the nature of the links between the participants and the Sponsor (Article L.1121-10 of the Public Health Code). The sponsor is also responsible for the compensation of the harmful consequences of the research for the person who undergoes it and for that of his or her dependents, unless it can be proved that the damage is not attributable to its fault or to that of any other party involved, without the possibility of invoking the act of a third party or the voluntary withdrawal of the person who initially agreed to undergo the research. Where the sponsor is not liable, the victims may be compensated under the conditions set out in Article L.1142-3.

The Forcilles-Fondation Cognacq-Jay hospital has taken out insurance under contract no. 163607 guaranteeing its civil liability as well as that of any intervening party with the company SHAM for the entire duration of the research, in accordance with article L.1121-10 of the Public Health Code.

13.5 Substantial amendment to the protocol

The investigator or coordinator informs the research commission of the Forcilles-Fondation Cogacq-Jay hospital of any proposed modification of the protocol. Any substantial modification will be submitted by the sponsor of this research to the CPP for its opinion.

13.6 Information note and express consent

In accordance with Article L.1122-1 of the Public Health Code, the information provided to the persons who are to be involved in the research is the subject of a written document submitted in advance to the personal protection committee. The ethical opinion of the CPP Ouest III has been requested.

The investigator at the centre offers the patient, or a relative if the patient is incapacitated, to participate in the study. The investigator informs the patient orally of the terms of the study and gives him/her the information note. If the patient gives free, informed and express oral consent to participate in the protocol, the information given orally and in writing, as well as the collection of oral consent, will be recorded in the patient's medical record.

In the event that a relative of the patient has given consent, as soon as possible, the patient will be informed of the research and asked for oral consent for the possible continuation of the research.

Patients are free to participate or withdraw from the study at any time in accordance with Article 21 of the GDPR. Data collected until the patient withdraws consent will be used unless the patient expressly requests otherwise. The withdrawal of consent by the patient and the agreement to use or not the data previously collected will be traced in the patient's medical file.

When the research is completed, the person who is to be the subject of the research may be informed of the overall results of the research in a manner to be specified in the information document.

13.7 Expected deadline for publication of results in an international journal

The deadline for the publication of the results is 30 months.

13.8 Data management

For each subject, an identification code (corresponding to the centre number-inclusion number-Initial Surname-Initial First Name) will be assigned. The data collected will be confidential and coded (only the identification code will appear). The concordance table linking the assigned identification code and the participant's name will be kept by the principal investigator in a file with computer restricted access rights. The data will be entered into a password protected Excel® file held by the principal investigator. Data processing and statistical analysis will be carried out at the Forcilles-Fondation Cognacq-Jay hospital.

The promoter is the owner of the data and no use or transmission to a third party can be made without his prior agreement.

The specific documents of a type 2 interventional research ("Loi Jardé", decree n° 2016-1537 of 16 November 2016, which came into force on 18 November 2016) with minimal risks and constraints will be archived by all parties for a period of 15 years after the end of the research. This indexed archive includes :

- successive versions of the protocol (identified by version number and date);
- correspondence ;
- the inclusion list or register ;
- the data collection document ;
- research-specific annexes ;
- the final report of the research.

The database used for the statistical analysis must also be archived by the person responsible for the analysis (paper or computer).

15.1 Appendix 1: CAM-ICU Confusion Assessment Score (26)

The score can only be used in patients who are able to open their eyes and shake hands on demand.

Criterion 1: Sudden onset and fluctuating course

Is the change in the patient's mental state sudden? (yes=positive/no=negative) Are there any fluctuations over the last 24 hours? (yes=positive/no=negative)

Criterion 2: Inattention

Does the patient have difficulty focusing attention?

ABRACADABRA" test: spell out each letter (1-2 seconds between each letter) and ask the patient to shake hands on the letter "A":

The test is positive if there are more than two errors (either the patient does not serve the hand on the letter A or serves it on another letter)

Criterion 3: Disorganised thinking

- YES/NO question
 - Does a stone float?
 - Are there fish in the sea?
 - Does one kilogram weigh more than two kilograms?

The test is positive if there is more than one wrong answer

- Verbal orders
 - Tell the patient: "Show me the same number of fingers" (Show two fingers)
 - Then "Do the same with the other hand".

The test is positive if the patient is wrong in these two commands

Criterion 4: Vigilance Assessment

Overall, how would you rate your patient's general condition? Alert, Vigilant, Lethargic, Stuporous, Comatose The test is positive if the level of awareness is other than alert

The diagnosis of delirium requires the presence of 3 of the 4 criteria. Criteria 1 and 2 are always required, together with criteria 3 or 4.

15.2 Appendix 2: MRC Score (28)

| RIGHT | Function | LEFT | | | |
|-----------|-------------------------------|------|--|--|--|
| | Shoulder abduction | | | | |
| | Elbow flexion | | | | |
| | Wrist extension | | | | |
| | Subtotal upper limbs (/15) | | | | |
| | Hip flexion | | | | |
| | Knee extension | | | | |
| | Ankle dorsal flexion | | | | |
| | Subtotal lower limbs (/15) | | | | |
| | SCORE | | | | |
| | Date://60 | | | | |
| Date://60 | | | | | |

Score assigned to each muscle group :

- 0 = no visible contraction
- 1 = visible contractions without limb movement
- 2 = insufficient movement to overcome weightlessness
- 3 = movements to overcome weightlessness
- 4 = movements against weightlessness and resistance
- 5 = normal muscle strength

